18.5 Elective admissions and supportive care

Elective admissions to hospital for patient convenience or for planned procedures or investigations or treatment as specified in this protocol and standard supportive care are not SAEs, and do not require SAE reporting.

19 PREGNANCY

Pregnancy testing is carried out as appropriate, as part of NHS Standard of Care prior to radiological scans. In the event a patient becomes pregnant within the study they will be withdrawn from the intervention (if applicable) and follow their standard clinical care. Patients will be offered the option of withdrawal from all active follow-up i.e. completion of questionnaires but allow continued collection of data from medical records that is recorded as part of routine standard care. This will allow them to be followed up by site until the end of the pregnancy.

20 STATISTICAL CONSIDERATIONS

20.1 Statistical Analysis Plan (SAP)

The statistical aspects of the study are summarised here with details fully described in a statistical analysis plan that will be drafted early in the trial and finalised prior to the final data lock. The SAP will be written by the Trial Statistician in accordance with the current OCTRU SOPs. The TSC and DSMC will review and, if necessary, provide input on the SAP.

A summary of the planned statistical analysis is included within this section.

20.2 Sample Size/Power calculations

We aim to recruit 952 participants over 32 months from at least 24 NHS centres. Data from the ENSURE study [15] indicated all-cause mortality rates in the standard-of-care arm of 55% at 3-years. Based on discussions with clinicians and patient representatives, a 10% absolute improvement in overall survival would be clinically meaningful to patients and would lead to change clinical practice. An absolute improvement in survival of 10% was also used in the recent CROSS and Neo-AEGIS trials [5,25]. The sample size calculations were based on a comparison of the survivor functions in the two groups using a two-sided log-rank test. The sample size was calculated based on statistical power of 90%, two-sided alpha=0.05 with a 3-year recruitment period and 3-year follow-up period and an expected all-cause 3-year mortality in the control group of 55% and an assumed improvement to 45% in the intervention group. This correspond to a hazard ratio of 0.749, assuming hazard rates are proportional. Allowing for a 10% loss to follow-up based upon average estimates from MAGIC and OEO2 trials in the UK [26, 27], 952 patients would need to be recruited to this trial, with approximately 273 all-cause mortality events occurring in the control arm and 229 events in the intervention arm.

Since the proposed translational sub-studies are intended to be hypothesis generating, no formal sample size calculations have been performed.

20.3 Choice of primary outcome/justification for the follow-up period

Following oesophageal and gastric cancer surgery, approximately 90% of cancer recurrences will occur in the first 3 years post surgery, with an often poor survival due to late presentation [15, 28, 29]. Thus the follow-up period of 3-years has been chosen to establish the value of intensive surveillance in detecting the vast majority of cancer recurrences at an earlier and potentially treatable stage.

20.4 Description of Statistical Methods

Results will be reported in line with the CONSORT statement.

All analyses will be carried out on the intention-to-treat population (i.e. all patients will be analysed in the group that they were randomised to regardless of the actual treatment received). It is not anticipated there will be any protocol deviations, however, in the event that any occur, we will

repeat the primary analysis for the per protocol population (patients excluded from the per-protocol population will be pre-specified in the SAP).

Standard descriptive statistics will be used to describe the demographics between the two follow-up regimens; reporting means and standard deviations or medians and inter-quartiles ranges as appropriate for continuous variables and numbers and percentages for binary and categorical variables. All comparative outcomes will be presented as summary statistics and reported together with 95% confidence intervals. All tests will be carried out at a 5% significance level.

It is anticipated that all statistical analysis will be undertaken using Stata (StataCorp LP, www.stata.com) or other well validated statistical software.

Primary outcome

The primary outcome is overall survival. An event is defined as death from any cause. Participants who have not died during the trial will have their survival time censored at their last known alive date. This includes participants who withdraw from the trial.

The primary outcome will be analysed using time-to-event methodology. Cox Proportional Hazards models will be used adjusting for minimisation factors (centre, age and pathological TNM stage). The hazard ratio and 95% confidence intervals will be reported. The assumption of proportional [11] hazards will be examined and if proportional hazards are not present alternative methods will be considered. Supplementary analysis will additionally adjust for other important prognostic factors, which will be pre-specified in the SAP. Kaplan Meier survival curves will be presented graphically and unadjusted log-rank tests will be undertaken for completeness. Disease specific survival and locoregional or distant tumour recurrence will be analysed using the same time-to-event techniques as for the primary outcome. HRQoI outcome measures (EORTC QLQ-C30 and QLQ-OG25 and CWS) will be compared between intervention arms as the dependent variable in a mixed-effects linear regression model with adjustment for the corresponding baseline score and the stratification factors. A random effect will be included to account for any heterogeneity is the response due to recruitment centre and fixed effects will be included to adjust for age and TNM stage, timepoint and a time-by-intervention interaction which will be included to take account of the repeated measures nature of the outcomes.

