16.3 Randomisation methodology

Consenting participants will be allocated randomly (1:1) to either the intensive surveillance arm or standard of care.

Randomisation will be performed using a minimisation algorithm to ensure balance between the two treatment groups using stratification factors:

• Recruiting centre

- Age (<50 years, 50-70 years, >70 years)
- Pathological TNM Stage (I & II, III & IV)

The first few participants will be randomised using a simple randomisation schedule, prepared by the trial statistician, to seed the minimisation algorithm, and a non-deterministic probabilistic element will be included to prevent predictability of treatment allocation. The randomisation schedule will be designed by the OCTRU study statistician.

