17.2 Data Collection

17.2.1 Baseline (within 12 weeks postoperatively) data collection

Sourced/collected by local study team Completed at hospital by local study team member from medical notes or with participant		Direct patient report
•	Participant demographics Blood test results Clinical staging results including CT findings before surgery Neoadjuvant therapy utilised Surgery performed and postoperative complications Intended adjuvant therapy	 Health-related quality of life questionnaires* EQ-5D-5L (unmodified) EORTC QLQ-C30 EORTC QLQ-OG25 Cancer Worry Scale (CWS) Healthcare Resource use questionnaire
•	Postoperative complications Pathological staging of cancer	

*QoL questionnaires will be completed prior to randomisation.

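### The primary Cox model stops at the minimisation factors, so baseline prognostic data already collected are left out of the deciding test, at a likely cost of a few points of power

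*Protocol*

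**What the plan says.** Section 20.4 defines the deciding analysis: "Cox Proportional Hazards models will be used adjusting for minimisation factors (centre, age and pathological TNM stage". It then says: "Supplementary analysis will additionally adjust for other important prognostic factors, which will be pre-specified in the SAP". So the protocol itself sets the order. The SAP is asked to name the covariates of the supplementary model, not to decide whether they belong in the primary one.

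The minimisation factors are defined only in section 16.3: recruiting centre, age in three bands cut at 50 and 70 years, and "Pathological TNM Stage (I & II, III & IV". Section 20.4 does not say in what form age and stage enter the model.

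Section 17.2.1 lists the baseline record. It includes demographics, pathological staging, the operation performed and "Neoadjuvant therapy utilised". Section 13.1.1 places randomisation after baseline data collection.

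Section 20.2 sizes the trial on a "comparison of the survivor functions in the two groups using a two-sided log-rank test", that is, without covariates.

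**The concern.** In a Cox model, prognostic variation that is left out pulls the estimated treatment hazard ratio towards 1, while the standard error hardly changes. Adjusting for strong baseline factors therefore raises power. Here the extra factors are already recorded, yet they enter only an analysis that does not decide the trial.

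Section 20.7 plans no formal comparative interim analysis, so there is one decisive test. The contrast may also start late: in the section 17.1 schedule the first CT is at month 6, and both arms have the same scheduled contact before then. A few points of power matter more in that setting than under an effect from day 0.

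**Working it through.** **1. The plan's own figure.** Inputs from section 20.2: "The sample size was calculated based on statistical power of 90%, two-sided alpha=0.05 with a 3-year recruitment period and 3-year follow-up period"; "expected all-cause 3-year mortality in the control group of 55% and an assumed improvement to 45% in the intervention group".

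- Hazard ratio: ln(0.55)/ln(0.45) = 0.7487, which matches the stated 0.749.
- Deaths (Schoenfeld): 4 × (1.960 + 1.2816)² / (ln 0.7487)² = 4 × 10.51 / 0.0838 ≈ 502. The protocol gives 273 + 229 = 502.
- Patients: with exponential survival, uniform 3-year accrual, 3 further years of follow-up and 10% loss per year, the probability of an observed death is 0.5747 (control) and 0.4822 (intervention), mean 0.5285. Then 502/0.5285 ≈ 950, against 952 planned. At 476 per arm the deaths are 273.6 and 229.5.
- Section 20.2 does not give the time unit of the 10% loss. The per-year reading reproduces the figures; a one-off inflation gives 874. The per-year reading is used below.

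The planned 90% is therefore the power of the unadjusted test.

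**2. Gain at the design effect (simulation A).** 952 patients, accrual and loss as above, 2,500 trials per setting, centre omitted, marginal 3-year mortality held at 55% v 45%. Assumed, because the protocol gives no values: stage III/IV in 45% with log-hazard ratio 0.7; age mean 66, SD 9, log-hazard ratio 0.015 per year; a further prognostic index with the residual log-hazard SD shown. All models were fitted to the same simulated trials. Gains are from unrounded values.

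| Residual SD | Unadjusted | Two-level stage, age bands | Stage, continuous age, index | Gain (points) |
|---|---|---|---|---|
| 0 | 90.3% | 92.8% | 93.1% | 0.2 |
| 0.3 | 89.8% | 92.5% | 94.0% | 1.4 |
| 0.5 | 89.3% | 92.1% | 95.8% | 3.7 |
| 0.7 | 89.4% | 91.7% | 97.7% | 6.0 |
| 0.9 | 89.5% | 91.1% | 98.8% | 7.7 |

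The SD 0 row isolates un-banding age: 0.2 points.

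*Hand check at SD 0.5.* The mean estimated hazard ratio moves from 0.739 to 0.718, so the log-hazard ratio grows by ln(0.718)/ln(0.739) = 0.3313/0.3025 = 1.095. Power of 92.1% corresponds to an expected z of 1.960 + 1.412 = 3.372. With the standard error unchanged, 3.372 × 1.095 = 3.69, and 3.69 − 1.96 = 1.73 gives about 95.8%, as simulated.

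**3. Four stage groups and a delayed effect (simulation B).** Same size, accrual and loss, 800 trials per setting, centre omitted. Assumed: 3-year survival by stage I–IV of 80/60/35/15% or 75/55/35/20%; stage mix 20/30/35/15%; SD of the other factors 0.3 or 0.5.

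| | Two-level stage | Four-level stage | Four-level + other factors | Total gain (points) |
|---|---|---|---|---|
| Effect from day 0 | 92–96% | 92–97% | 94–99% | 1.6–4.6 |
| No effect before month 6 | 70–75% | 71–77% | 77–82% | 5–7 |

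Four-level stage alone adds 0.5 to 2.5 points. Simulation error is about 1 to 2 points per power figure. A smaller run (C, 500 trials per setting, same stage survivals and SDs) gave 0 to 3 points for four-level stage alone. With the other factors it gave 2 to 4 points (day 0) and 5 to 10 points (delayed).

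**The case against.** The strongest reply is that nothing here is wrong. Pre-specified adjustment for the minimisation factors is conventional, and in simulation A that model already has about 91 to 93% power against a 90% target. This stands: the point is a missed gain, not an error or contradiction.

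Second, banded entry is inferred. Section 20.4 names the factors without their coding, and coding can be settled in the SAP. This also stands, but it touches only the 0 to 3 points from uncollapsing. That other factors are merely supplementary is stated outright.

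Third, the extra factors may be weak. No document shows how much neoadjuvant therapy adds beyond stage and age, and tumour site is not a listed baseline item; it could at best be read from the operation performed. The size of the gain is therefore conditional on assumptions.

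Fourth, the change is not free. The hazard ratio becomes conditional on more covariates: 0.731 and 0.719 at SD 0.3 and 0.5 in simulation A, against "This correspond to a hazard ratio of 0.749, assuming hazard rates are proportional". The current model already departs from that value (0.739), so this is a matter of degree. Missing baseline values also need a rule.

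A reader might infer that the plan gives up as much as ten points for nothing. The documents do not support that. From 91 to 93%, only 7 to 9 points remain to 100% at the design effect. Ten points appeared only as the top of the delayed-effect range in run C, and simulation B did not reproduce it. Reading 0.749 as the conditional hazard ratio gives larger gains (12.3 points at SD 0.7), but the marginal effect is then weaker than the stated 55% v 45%.

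Nor do the 70 to 75% figures show that the trial is underpowered. They rest on an assumed six-month delay, and section 20.4 already foresees alternative methods if hazards are not proportional.

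**Conclusion.** The point holds as a cheap improvement. The protocol confines the deciding model to the minimisation factors and leaves baseline information unused in the primary test. The likely gain from a fuller model is about 1.5 to 5 points of power at the design effect, and about 5 to 7 points if nothing happens before month 6. Both figures assume a residual log-hazard SD of 0.3 to 0.5 and 10% loss per year, and omit centre. Most of the gain depends on the strength of the extra factors. The direction is consistent across all the runs; the size is uncertain. Neither the validity of the primary analysis nor the planned 90% power is in question.

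**What to change.** In section 20.4, state that the primary Cox model adjusts for centre, age as a continuous variable, pathological stage in its uncollapsed form and neoadjuvant therapy, plus tumour site if it is recorded at baseline. Fix the list and the coding before any data by arm are seen. Keep the model with the minimisation factors alone, and the unadjusted log-rank test, as supplementary analyses.

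The cost is wording in the protocol and SAP: no added patients or visits, and no new data unless tumour site has to be added to the baseline form. Two sentences should go with it: one saying that the reported hazard ratio is conditional on these covariates and so is not directly the design value of 0.749, and one giving a simple rule for missing baseline values. If the sponsor keeps the present primary model, section 20.4 should at least say in what form age and stage enter it.

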9.3 Secondary objectives and outcome measures

Objectives	Outcome measures	Time point(s) of evaluation of this outcome measure (if applicable)	Data required	Source data (including location)
 To determine the impact of intensive surveillance upon the detection and treatment of 	a) Disease-specific mortality, defined as known oesophageal or gastric cancer recurrence at the time of death.	3 years post- randomisation of the last included participant.	Cause of death Date of death Last date known alive and oesophageal or gastric cancer recurrence free.	Participant's medical notes.
cancer recurrence.	 b) Pattern of tumour recurrence, defined as the incidence of loco- regional or distant recurrence. c) Treatment of 	3 years post- randomisation of the last included participant. 3 years post-	Site of recurrence as defined as loco- regional, distant or mixed. Treatment of	Participant's medical notes including CT reports. Participant's medical
	tumour recurrence,	randomisation of	recurrence as	notes.

		ie. the requirement for chemotherapy, surgery, immunotherapy, radiotherapy, chemoradiotherapy, best supportive care or other as determined by the clinical team at the treating site.	the last included participant.	allocated, along- with compliance to and completion of treatment.	
		d) Rates of oligometastatic (one site) tumour recurrence.	3 years post- randomisation of the last included participant.	Site of recurrence as defined as oligometastatic.	Participant's medical notes including CT reports.
		e) Rates of multi- metastatic (several sites) tumour recurrence.	3 years post- randomisation of the last included participant.	Site of recurrence as defined as multi- metastatic.	Participant's medical notes including CT reports.
2.	To determine the impact of surveillance upon health- related quality of life.	HRQoL, including anxiety or depression and worry of cancer returning as measured by the following validated questionnaires: EQ- 5D-5L, EORTC QLQ- C30 and QLQ-OG25 and Cancer Worry Scale (CWS).	At baseline, 6, 12, 18, 24, 30 and 36 months post- randomisation.	EQ-5D-5L EORTC QLQ-C30 EORTC QLQ- OG25 CWS.	Participant-reported outcome (questionnaires administered and data collected centrally).

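### Kaplan-Meier curves carried over from all-cause death would overstate the incidence of recurrence and disease-specific death, because these secondary outcomes have competing events

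*Protocol*

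**What the plan says.** Protocol section 20.4 fixes the method for the secondary time-to-event outcomes in one sentence: "Disease specific survival and locoregional or distant tumour recurrence will be analysed using the same time-to-event techniques as for the primary outcome".

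The primary techniques, in the same section, are:
- a Cox model adjusted for centre, age and pathological TNM stage, reported as a hazard ratio with 95% CI;
- curves and a test: "Kaplan Meier survival curves will be presented graphically and unadjusted log-rank tests will be undertaken for completeness";
- the event: "An event is defined as death from any cause";
- the censoring rule: "Participants who have not died during the trial will have their survival time censored at their last known alive date".

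Section 9.3 defines the outcomes to which these techniques are carried over. Item (a) is "Disease-specific mortality, defined as known oesophageal or gastric cancer recurrence at the time of death". Item (b), the pattern of recurrence, is "defined as the incidence of loco- regional or distant recurrence", and the site is to be recorded as loco-regional, distant or mixed.

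The protocol does not mention competing risks, cumulative incidence or cause-specific hazards, and gives no rule for participants who die without recurrence.

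**The concern.** Nothing can prevent death from any cause from being observed except the end of follow-up, so Kaplan-Meier is the right estimator for the primary outcome. The secondary outcomes differ. A participant who dies without known recurrence can never become a disease-specific death or a recurrence. If recurrence patterns are analysed separately by first site, a first recurrence of one pattern also rules out a first recurrence of another.

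Kaplan-Meier with such participants censored treats them as still able to have the event later. Its complement then estimates risk in a hypothetical setting without the competing events, which is higher than the proportion who actually have the event. Section 9.3 asks for that proportion, since it names incidence as the outcome.

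These outcomes serve the first secondary objective, the effect of surveillance on detection and treatment of recurrence. The disease-specific definition depends on recurrence being known at death, and the intervention is meant to change what is known. An equal bias in the two arms therefore cannot be taken for granted.

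**Working it through.** **The plan's own figures.** The protocol gives no expected figure for the secondary outcomes. Its primary calculation (section 20.2) reproduces and does not involve them:
- HR = ln(0.55)/ln(0.45) = 0.749.
- Events (Schoenfeld, 90% power, two-sided 0.05) = 4 × (1.960 + 1.282)² / (ln 0.7487)² = 502. The stated 273 + 229 is also 502.

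**Inputs for the illustration.** Three-year mortality of 55% (control) and 45% (intervention) comes from section 20.2. All cause-specific shares and hazards below are assumptions, taken as constant over time.

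**1. Disease-specific death.** Let p be 3-year all-cause mortality and s the share of the death hazard that is other-cause.
- Cumulative incidence = p(1 − s)
- One minus Kaplan-Meier = 1 − (1 − p)^(1 − s)

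| Arm | s | 1 − KM | Incidence | Excess (points) |
|---|---|---|---|---|
| Control, p = 0.55 | 5% | 53.2% | 52.2% | 0.9 |
| | 10% | 51.3% | 49.5% | 1.8 |
| | 20% | 47.2% | 44.0% | 3.2 |
| | 30% | 42.8% | 38.5% | 4.3 |
| Intervention, p = 0.45 | 5% | 43.3% | 42.7% | 0.6 |
| | 30% | 34.2% | 31.5% | 2.7 |

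The absolute contrast between arms shifts as well. With s = 20% in both arms, Kaplan-Meier gives 47.2% − 38.0% = 9.2 points, against a true 44.0% − 36.0% = 8.0 points.

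**2. Any recurrence as one composite.** Only death without recurrence competes. Let a be the recurrence hazard and b the competing hazard, per year.
- One minus Kaplan-Meier at 3 years = 1 − exp(−3a)
- Cumulative incidence = a/(a + b) × [1 − exp(−3(a + b))]
- a = 0.25, b = 0.05: 52.8% against 49.5%, an excess of 3.3 points.
- a = 0.25, b = 0.08: 52.8% against 47.6%, an excess of 5.2 points.

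**3. Locoregional recurrence by first site (conditional on that definition).** The formulas are the same, but b now also includes first recurrence of another pattern.

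| a | b | 1 − KM | Incidence | Ratio |
|---|---|---|---|---|
| 0.05 | 0.20 | 13.9% | 10.6% | 1.32 |
| 0.06 | 0.25 | 16.5% | 11.7% | 1.41 |
| 0.08 | 0.20 | 21.3% | 16.2% | 1.31 |
| 0.08 | 0.25 | 21.3% | 15.2% | 1.40 |

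**4. Cross-check with a different anchor.** Take 60% with any recurrence by 3 years. This is an assumption, suggested by the section 8 figure for recurrence and death. With a locoregional-first share of 20% to 40% and 0% to 10% dying without recurrence, the locoregional ratio is 1.28 to 1.55. At a 30% share and 5% deaths, one minus Kaplan-Meier is 25.2% for locoregional (true 18.0%) and 49.3% for distant (true 42.0%). The two sum to 74.5% when only 60% have recurred.

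**The case against.** The strongest defence has four parts.

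*The main comparison is sound.* The lead technique is the adjusted Cox model. With competing events censored, it and the log-rank test remain valid for the cause-specific hazard. This stands. A reader might infer that the whole secondary analysis is invalid or that the hazard ratios are biased, but the protocol does not support that. The defect lies in using Kaplan-Meier as an incidence estimate.

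*The error is inferred.* The written censoring rule sits under the primary outcome and concerns people who have not died; no rule is written for death without recurrence. Section 20.1 calls the section a summary, with details left to the SAP. This stands in part. However, section 20.4 states the method for these outcomes outright, without deferring it, and it includes Kaplan-Meier curves. Applied unchanged to an outcome defined as incidence, it leads to the overstatement.

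*First site is not in the definition.* Section 9.3 does not say first recurrence and allows a mixed category, and section 20.4 can be read as one composite of locoregional or distant recurrence. This stands. A reader might take the ratio of about 1.4 as the expected error for locoregional recurrence. It applies only under a first-site analysis and assumed hazards. Under the composite reading, only death without recurrence competes.

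*The consequences are limited.* A reader might expect the inflated incidence to reach the economic results. Section 20.12 gives no support for that: the within-trial analysis uses EQ-5D, survival time and resource use, not recurrence incidence. Treatment of recurrence and the oligometastatic and multi-metastatic rates (section 9.3, items c to e) are not assigned to these techniques in section 20.4.

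**Conclusion.** The point holds for the Kaplan-Meier part of the sentence. Followed as written, it would present curves whose complement exceeds the incidence named as the outcome whenever competing events occur.

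The direction is certain; the size rests on assumed constant hazards and shares:
- about 1 to 4 points for disease-specific death in the control arm (other-cause share 5% to 30% of 55% mortality), and little if other-cause deaths are few;
- about 3 to 5 points for any recurrence (0.25 per year against 0.05 to 0.08 per year);
- a ratio of about 1.3 to 1.4 for locoregional recurrence, only if analysed by first site.

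Whether the arms would be affected unequally cannot be determined from the protocol. Only secondary outcomes are involved. The change should be made, but it does not threaten the trial's main conclusion.

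**What to change.** In section 20.4, replace the sentence on disease-specific survival and recurrence with text that does three things:

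1. Names the competing events for each outcome: death without known recurrence for disease-specific death and for recurrence and, if patterns are analysed separately by first site, first recurrence of another pattern. It should say whether first site is meant and how mixed recurrence is classed.
2. Makes Aalen-Johansen cumulative incidence by arm the incidence estimate in place of Kaplan-Meier, with the 36-month difference between arms and its 95% CI.
3. Keeps the adjusted Cox models and labels their results as cause-specific hazard ratios.

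The cost is a few sentences in the protocol, matched in the SAP, before data lock. The methods are standard in the named software. Recurrence type and the date and cause of death are already collected (section 17.2.2), as is the timing of recurrence (section 10.2). No new data and no change to the sample size are needed.

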10 STUDY DESIGN AND SETTING

The SARONG study is a multi-centre, open-label, two-arm, parallel design, superiority randomised controlled trial. 952 patients (476 in each of two trial arms) will be recruited from approximately 24 sites in the UK. Participants will be randomised to either intensive surveillance (including radiological scans) every 6 months for 36 months and an endoscopy at 12 months post-randomisation or standard care follow-up for 36 months.

A study flow chart is provided in APPENDIX 1 – STUDY FLOW CHART.

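### The HRQoL model in section 20.4 relies on a fixed time-by-arm interaction to handle repeated measures and names no participant-level term, so an arm effect averaged over visits would have too small a standard error

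*Protocol*

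**What the plan says.** Protocol section 20.4 analyses the EORTC QLQ-C30, QLQ-OG25 and Cancer Worry Scale scores with a "mixed-effects linear regression model with adjustment for the corresponding baseline score and the stratification factors". It then lists the terms:

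- Random part: "A random effect will be included to account for any heterogeneity is the response due to recruitment centre".
- Fixed part: age, TNM stage, timepoint, and "a time-by-intervention interaction which will be included to take account of the repeated measures nature of the outcomes".

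No participant random effect, residual covariance across visits or cluster-robust standard error is named. The section does not say whether the reported HRQoL comparison is an average over visits, a difference at each visit, or the interaction test.

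Section 9.3 sets the HRQoL schedule: "At baseline, 6, 12, 18, 24, 30 and 36 months post- randomisation". Baseline enters as a covariate, so a participant contributes up to six outcome values. On the error rate, section 20.4 states: "All tests will be carried out at a 5% significance level".

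**The concern.** The interaction is given a task that it cannot do. A fixed time-by-arm term describes how the mean difference between arms moves over the visits. It says nothing about how closely one person's scores at 6, 12 and 18 months resemble each other. The centre effect captures only what patients at the same hospital share. With those terms alone, six scores from one person carry the weight of six scores from six people.

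HRQoL is part of the trial's aim (section 9.1). The background section calls HRQoL, including anxiety, a key secondary outcome because earlier findings on anxiety under intensive surveillance disagreed. A spurious overall difference in worry or anxiety, or a missed divergence over time, would bear directly on that question.

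**Working it through.** **Inputs from the protocol.** Six post-baseline visits, so m = 6 (section 9.3); 5% two-sided level (sections 20.4 and 20.9); 952 participants in two equal arms (section 10); about 24 centres (section 10).

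**Assumed input.** The protocol gives no within-person correlation, standard deviation or power for any HRQoL score. I take an exchangeable correlation ρ of 0.3, 0.5 and 0.7.

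**Step 1: arm effect averaged over visits.** Let each score have residual variance σ². The mean of m scores from one person has variance σ²[1 + (m − 1)ρ]/m. A model that treats them as independent uses σ²/m. The true-to-model variance ratio is therefore 1 + (m − 1)ρ, which is 1 + 5ρ for complete data. The real type I error of a nominal 5% test is 2[1 − Φ(1.96/√(1 + 5ρ))]. At ρ = 0 this returns the protocol's own 5%.

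| Residual ρ | 1 + 5ρ | True SE / model SE | Type I error |
|---|---|---|---|
| 0 | 1.0 | 1.00 | 5% |
| 0.3 | 2.5 | 1.58 | 21.5% |
| 0.5 | 3.5 | 1.87 | 29.5% |
| 0.7 | 4.5 | 2.12 | 35.6% |

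**Step 2: allowing for baseline adjustment.** The model adjusts for the baseline score, which removes part of the within-person correlation. If ρ is the raw exchangeable correlation, the residual correlation given baseline is (ρ − ρ²)/(1 − ρ²) = ρ/(1 + ρ).

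| Raw ρ | Residual ρ/(1 + ρ) | 1 + 5 × residual | True SE / model SE | Type I error |
|---|---|---|---|---|
| 0.3 | 0.23 | 2.15 | 1.47 | 18% |
| 0.5 | 0.33 | 2.67 | 1.63 | 23% |
| 0.7 | 0.41 | 3.06 | 1.75 | 26% |

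**Step 3: fewer visits.** Death and dropout shorten the series. With four scores per person the ratio is 1 + 3ρ. The type I error is then 15.5% at residual ρ = 0.3 and 26.6% at 0.7. The inflation shrinks but remains.

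**Step 4: change over time.** For the difference between two visits, the true variance is proportional to 1 − ρ while the model uses 1. The type I error is 2[1 − Φ(1.96/√(1 − ρ))], which gives 1.9%, 0.6% and 0.03% at ρ = 0.3, 0.5 and 0.7. The test is conservative, so it loses power.

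**Step 5: one visit at a time.** Each participant contributes one value per visit, so within-person correlation does not enter and the error stays near nominal.

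**Step 6: simulation check.** No true effect, 952 participants, 24 centres, six visits with attrition, baseline as covariate, arm-by-visit fixed effects, variance components treated as known, 400 runs per ρ. Each cell gives the rejection rates at ρ = 0.3, 0.5 and 0.7.

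| Test | Centre random effect only | Participant intercept added |
|---|---|---|
| Average over visits | 19%, 27%, 34% | 5.0%, 5.5%, 5.3% |
| Month 6 | 5.8%, 6.5%, 6.3% | 6.0%, 7.3%, 6.0% |
| Month 36 | 4.5%, 4.8%, 5.0% | 4.8%, 5.5%, 4.5% |
| Time-by-arm, 5 df | 1.3%, 0.3%, 0% | 3.8%, 4.5%, 4.0% |

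With 400 runs, the Monte Carlo standard error near 5% is √(0.05 × 0.95/400) = 1.1 percentage points. The single-visit rates therefore cannot be told apart between the two models. The simulation agrees with the formulas in direction and approximate size.

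**The case against.** The best defence is that section 20.1 presents section 20 as a summary and leaves full detail to a SAP that is not shown. A participant intercept or a residual covariance is the sort of detail a SAP supplies. Section 20.4 calls the model mixed-effects, shows that the authors had repeated measures in mind, and does not say that centre is the only random effect. This stands as far as it goes: the absence of a covariance structure alone would not be a finding. The protocol goes further, however, and assigns the repeated-measures role to a term that cannot fill it. A SAP that follows the text literally inherits the fault; one that corrects it departs from the stated reasoning.

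A second objection is that a time-by-arm interaction leads naturally to visit-specific differences, and those are about right. This also stands. A reader might infer that all HRQoL standard errors are too small, or that false-positive HRQoL findings are likely in general. The document does not support either reading. Of the three candidate contrasts, one is inflated, one is near nominal and one is conservative, and section 20.4 does not say which will be tested.

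Third, all the sizes rest on an assumed correlation, and baseline adjustment lowers it. That is why step 2 gives the smaller range beside the larger one.

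**Conclusion.** The statement in section 20.4 is wrong as written: the interaction does not account for repeated measures, and no named term does. If the model is fitted as described and an arm effect averaged over visits is reported, its standard error is too small. The factor is about 1.6 to 2.1 for a residual correlation of 0.3 to 0.7, or about 1.5 to 1.75 if those values are raw correlations. These figures assume complete data and an exchangeable correlation. The time-by-arm test would be under-sensitive, and single-visit comparisons would be about right.

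The point is of moderate weight. It concerns secondary outcomes only. A reader might extend it to the trial's main result, but the primary survival analysis and the 952 participants rest on a log-rank calculation that uses no HRQoL input. A reader might also want a rule here for scores after death; that is a separate question, and section 20.10 leaves missing-data handling to the SAP.

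**What to change.** In section 20.4, and carried into the SAP:

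1. Add a participant-level random intercept nested in centre, or an explicit within-participant residual covariance across visits. Either addresses the fault. The random intercept alone brought the averaged test back to about 5% in the simulation, which used an exchangeable correlation.
2. Describe the time-by-intervention interaction as allowing the effect to differ by visit, and drop the claim that it accounts for the repeated measures.
3. Name the HRQoL contrast to be tested: the average over visits, the difference at a stated visit, or the interaction.

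The cost is a sentence or two of text. Data collection, sample size and patient burden do not change.
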